3. STUDY OBJECTIVE AND TASKS

Primary objective of the study:

1. To confirm that the PK indices of the IMP BP-SCIG 20% are comparable with those of the BIOVEN product.
2. To confirm the adjustment factor for the dose of BP-SCIG 20% to ensure a steady-state area under the concentration-time curve (AUC) for the total IgG level, which is non-inferior to the values of BIOVEN, the drug of previous therapy.
3. To confirm that the threshold IgG levels (in administration of the IMP BP-SCIG 20% to patients with PID in a monthly dose of 0.4–0.8 g/kg, under a once a week regimen) are non-inferior compared to threshold IgG levels on previous therapy (in patients previously receiving human normal immunoglobulin products intravenously or another product of human normal immunoglobulin for subcutaneous administration), or those reported in the literature (in treatment-naïve patients).
4. Assessment of the efficacy, tolerability, safety, and pharmacokinetic parameters of BP-SCIG 20% in long-term use in patients with primary immunodeficiency with impaired antibody production.

Additional pharmacokinetic assessment objectives:

- To confirm the adjustment factor for the dose of BP-SCIG 20% to ensure a steady-state area under the concentration-time curve (AUC) for the total IgG level, which is non-inferior to the values of BIOVEN, the drug of previous therapy.
- To assess the variability of trough IgG levels in children and adolescents compared with adult patients.
- To determine the pharmacokinetic parameters (Cmax, AUC0-t, AUC0-∞, Tmax, t1/2, Kel, IR, Cl, AUCextrapol, Vd) for the IMP BP-SCIG 20% in 20 adult patients with PID, and compare them with the available published literature.
- To compare the results of pharmacokinetic data for patients who have not previously received human normal immunoglobulin products with published literature (descriptively).
- To compare the results of pharmacokinetic parameter study (Cmax, AUC0-t, AUC0-∞, Tmax, t1/2, Kel, IR, Cl, AUCextrapol, Vd) between the cohorts.

Safety and tolerability assessment tasks

- Conduct an interim safety assessment for the first 10 patients enrolled in the study who must be adults and must have received at least 4 IMP administrations.

Based on the results of such assessment (*interim report*), the possibility of enrolling patients younger than 18 years of age is determined;

- Assess the frequency of adverse events;
- Assess the incidence of adverse reactions to the IMP;

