For Cohort C, newly diagnosed (treatment-naïve) patients are required to undergo Visit 1 of the screening period; if meeting inclusion/non-inclusion criteria, the patient proceeds to treatment with the IMP BP-SCIG 20%, starting from Cycle 1.

Table 4.2.2 Schedule of Procedures at Week 21 – Pharmacokinetic assessment of the IMP

Structure of PK assessment*		
No.	PK point	Description
1	PK0 (pre-administration)	Before IMP administration (10–30 min prior)
2	PK1 (30 min)	30 minutes after IMP administration (± 10 min)
3	PK2 (3 hours)	3 hours after IMP administration (± 30 min)
4	PK3 (1 day)	24 hours after IMP administration (± 5 h)
5	PK4 (2 days)	48 hours after IMP administration (± 5 h)
6	PK5 (3 days)	72 hours after IMP administration (± 5 h)
7	PK6 (4 days)	96 hours after IMP administration (± 5 h)
8	PK7 (7 days, threshold)	After 7 days (± 5 h), before the next administration of the IMP

* – The points for pharmacokinetic assessment of BP-SCIG 20% were selected in accordance with the available data on achieving Cmax following subcutaneous administration of the MPs belonging to the subcutaneous immunoglobulin category, and for the purpose of clear demonstration of differences in concentration-time curves for IVIG and SCIG.

Table 4.2.3. Schedule of procedures at Visit 3 – Pharmacokinetic assessment of IVIG

Structure of PK assessment**		
No.	PK point	Description
1	PK0 (pre-administration)	Before administration of BIOVEN (10–30 min prior)
2	PK1 (15 min)	15 minutes after administration of BIOVEN (± 10 min)
3	PK2 (1 hour)	1 hour after administration of BIOVEN (± 15 min)
4	PK3 (1 day)	24 hours after administration of BIOVEN (± 5 h)
5	PK4 (3 days)	72 hours after administration of BIOVEN (± 5 h)
6	PK5 (7 days)	7 days after administration of BIOVEN (± 5 h)
7	PK6 (14 days)	14 days after administration of BIOVEN (± 5 h)
8	PK7 (21 days)	21 days after administration of BIOVEN (± 5 h)
9	PK8 (28 days)	28 days after administration of BIOVEN (± 5 h) (where applicable***)

**The points for pharmacokinetic assessment of BIOVEN were selected based on previous PK studies of BIOVEN.

***Interval between the administrations (every 21–28 days) of BIOVEN, used as a prior therapy, is determined individually for each patient in accordance with the approved instructions for medical use.

4.3. Randomisation and blinding.

No randomisation or blinding is used in this clinical trial.

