9.6 Assessment of pharmacokinetic data

Analysis of pharmacokinetic parameters.

The main pharmacokinetic parameters include:

1. AUC-t value. Steady-state area under the concentration-time curve (AUC) for the total IgG level shall be compared with the values for the prior therapy (BIOVEN) for the relevant patient cohorts.
2. Trough IgG levels. The monthly trough IgG levels obtained, measured after 4 months of treatment with the IMP, prior to the next infusion, once every 4 weeks, over 6 months, shall be compared with the trough levels for at least two prior infusions of the previous SCIG or IVIG product. For treatment-naïve patients, a descriptive comparison with the data in published literature (if available) is required.

Methods of descriptive statistics: n, arithmetic mean, standard deviation, the median and the percentiles, the minimum and maximum values (depending on the type of distribution), including the plotting of graphs and charts and methods of interval estimation.

To evaluate the significance of changes over time in the event of assessing the parameter at two visits (before and after) in the case of quantitative variables, the analysis will use Student's t-test for paired data or Wilcoxon signed rank test – depending on the results of checking the normality of the distribution of difference [after - before] using the Shapiro-Wilk test. In order to assess changes over time in the event of measuring variables at more than two visits, methods of one-way analysis of variance (ANOVA) with subsequent application of post hoc analysis using Tukey's test will be used. In order to compare by those variables, by which the data were heterogeneous at baseline, covariance analysis (ANCOVA) will be used. In order to check the preconditions for the use of analyses of variance and covariance, the normality of distribution of the data and their residuals will be tested using the Shapiro-Wilk test. If the residuals are not distributed normally, or if the data do not pass the normality check, a corresponding rank analysis will be performed.

For the Shapiro-Wilk test, the significance level will be set at 0.01, and for other tests it will be set at 0.05. If a multiple comparisons effect occurs, significance level adjustments will be applied using the Holm method or Benjamini-Hochberg method.

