9.10 Conclusion regarding non-inferiority

Conclusion on non-inferiority shall be made by the primary efficacy variable using a confidence interval-based approach.

For the primary efficacy variable, the null hypothesis H0 is that the frequency of serious bacterial infection cases is 1.0 or greater per patient per year. The alternative hypothesis H1 is that the frequency of serious bacterial infection cases is less than 1.0 per patient per year. The null hypothesis is rejected if the upper limit of the 99 % confidence interval is less than 1.0 case of serious bacterial infection per patient per year. Then it will be considered that the investigational route of administration of the drug (SCIG manufactured by BIOPHARMA PLASMA LLC) is non-inferior in terms of efficacy compared to the literature data on the level of efficacy of existing SCIG products and compared to the efficacy of BIOVEN use.

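### Non-inferior AUC and comparable PK against BIOVEN are primary objectives, but the AUC comparison is given only a paired test of difference, with no margin, no decision rule and no common AUC interval

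*Protocol*

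**What the plan says.** Section 3 lists among the primary objectives "To confirm that the PK indices of the IMP BP-SCIG 20% are comparable with those of the BIOVEN product" (objective 1) and a steady-state AUC for total IgG "which is non-inferior to the values of BIOVEN, the drug of previous therapy" (objective 2). Neither objective carries a margin or a range.

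Section 9.6 names AUC and trough IgG as the main PK parameters. On AUC it says: "Steady-state area under the concentration-time curve (AUC) for the total IgG level shall be compared with the values for the prior therapy (BIOVEN"). The inference for a parameter measured twice is introduced with "To evaluate the significance of changes over time in the event of assessing the parameter at two visits (before and after") and is a Student's "t-test for paired data or Wilcoxon signed rank test", chosen by a Shapiro–Wilk check. On the level, apart from Shapiro–Wilk: "for other tests it will be set at 0.05". More than two visits go to one-way ANOVA with Tukey's test, with ANCOVA or rank analysis in some cases. Interval estimation appears once, in the list of descriptive methods, without a confidence level or an acceptance limit. Section 9.3 exempts PK from its statement that no inferential analysis is planned.

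Section 9.10 contains the only non-inferiority rule: "Conclusion on non-inferiority shall be made by the primary efficacy variable using a confidence interval-based approach". That variable is the rate of serious bacterial infections.

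Section 9.2 sets the adult cohorts at 8–10 patients, from a cited range of 6–12. Section 9.7 defines AUC0-t as running to the last quantifiable sample. Tables 4.2.2 and 4.2.3 place that sample at 7 days for the study product and at 21 or 28 days for BIOVEN.

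**The concern.** Objective 2 asks whether exposure on the new product is not meaningfully lower than on BIOVEN. The named test asks whether the mean difference can be distinguished from zero. A non-significant result does not answer the first question, and it becomes more likely as patients become fewer or the data noisier. A significant result does not answer it either, because no size of difference has been declared unacceptable.

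Two primary objectives are affected. The same BIOVEN data are to be used to confirm or recalculate the dose adjustment factor (sections 4.2 and 6.3.9), so it matters how the AUC comparison is read. The two AUCs as defined also cover different lengths of time, and then the test would not compare exposure at all.

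**Working it through.** **The plan's own figure.** The protocol gives no PK power, SD or margin, so there is no calculation to reproduce. The 8–10 per adult cohort simply falls inside the cited range of 6–12.

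**Inputs from the protocol.** n = 8–10 (section 9.2); paired test at 0.05 (section 9.6). Sidedness is not stated; two-sided is assumed.

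**Assumed inputs.** Within-patient CV of AUC 10–25%; true AUC ratio 0.85 or 0.80; for the alternative rule, a margin of 0.80. AUC is taken on a common time basis.

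**Step 1: chance that a true deficit is non-significant.** The SD of the within-patient log difference is s = √2 × √ln(1 + CV²), which gives 0.141, 0.211, 0.280 and 0.348 at CV 10, 15, 20 and 25%. The non-centrality is ln(ratio) × √n / s. The chance of p > 0.05 is the non-central t probability between ±t(0.975, n−1).

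Example: ratio 0.85, CV 15%, n = 8. Non-centrality = −0.1625 × 2.828 / 0.211 = −2.18; critical value 2.365; probability 0.53.

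| CV | 15% deficit, n=8 / n=10 | 20% deficit, n=8 / n=10 |
|---|---|---|
| 10% | 20% / 10% | 3% / 1% |
| 15% | 53% / 42% | 27% / 16% |
| 20% | 70% / 63% | 51% / 39% |
| 25% | 79% / 74% | 65% / 56% |

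A simulation of the full rule (Shapiro–Wilk at 0.01, then t-test or Wilcoxon on raw differences; 3,000 runs per cell; between-patient log-SD 0.25 assumed) gives similar or slightly higher values. For a 15% deficit at CV 15% they are 57% / 45%; for a 20% deficit at CV 20% they are 54% / 43%.

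**Step 2: a rule that does address non-inferiority.** Conclude non-inferiority if the lower limit of the 90% CI for the geometric mean ratio is at or above 0.80. At a true ratio of 0.80 this passes in 5% of trials at any CV. At a true ratio of 1.00 the non-centrality is −ln(0.80) × √n / s and the critical value is t(0.95, n−1):

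| CV | Success at true equality, n=8 / n=10 | n for 80% |
|---|---|---|
| 10% | 99% / 100% | 5 |
| 15% | 85% / 92% | 8 |
| 20% | 65% / 75% | 12 |
| 25% | 50% / 59% | 17 |

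**Step 3: the time basis.** At equal average IgG, AUC is proportional to the sampling interval. A literal comparison of AUC0-t gives 7/28 = 0.25 to 7/21 = 0.33. A paired test on those values would probably be significant whatever the product does, so the figures in step 1 apply only once AUC is normalised.

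**The case against.** **The analysis plan may settle this.** Margins, confidence levels and the log scale are often left to that document. This stands for the detail. But the protocol has already chosen the method for the two-visit comparison, and that method does not fit the objective. A later plan would have to depart from section 9.6 to repair it.

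**Section 9.6 names more than the paired test.** This is true. ANOVA with Tukey's test is also a test of difference and applies to parameters measured at more than two visits, such as monthly troughs. Interval estimation is descriptive there and has no limit attached.

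**No passage says that non-significance means success.** A reader might infer that a non-significant p-value will be taken as proof of non-inferiority. The documents do not say so: the PK decision rule is undefined. A reader might also infer that a real deficit would often be missed. That depends on a CV the protocol does not give; at CV 10% the miss rates are low.

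**A trivial difference failing in a large set.** A reader might extend the argument to 40 patients. Forty is the minimum for troughs, which are repeated over several visits, so no planned AUC comparison has that size.

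**Weight of AUC.** Section 4.1 makes trough IgG the primary PK endpoint and lists the dose-factor aim and AUC as secondary. Section 3 nevertheless puts non-inferior AUC among the primary objectives, so the inconsistency does not remove the point.

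**Cmax and Tmax.** Table 4.2.2 says sampling times were chosen "for the purpose of clear demonstration of differences in concentration-time curves for IVIG and SCIG". A reader might see a contradiction with objective 1. Different curve shapes are compatible with comparable exposure, so this shows only that objective 1 should say which indices it means.

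**Conclusion.** The point holds as a mismatch between objective and method. For AUC, section 9.6 prescribes a test of difference where section 3 claims non-inferiority, and the protocol gives no margin or other rule from which that claim could be drawn. This conclusion needs no assumption about variability.

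Its size does. Under the assumptions listed, with 8–10 adults, a true 15% deficit is more likely than not to be non-significant once the within-patient CV exceeds about 14–17%; for a 20% deficit the threshold is about 20–23%.

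The undefined time basis is a separate defect in the same comparison and has to be settled first. The documents do not support saying that the sponsor will count a non-significant result as success; they support saying that how objective 2 would be judged is open.

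**What to change.** In section 9.6:

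- State that AUC is normalised to a common interval for both products, for example AUC per week.
- State that it is compared within patients on the log scale, as the geometric mean ratio of BP-SCIG 20% to BIOVEN with a 90% CI.
- Conclude non-inferiority only if the lower limit is at or above a margin fixed in advance (0.80 is an example; the sponsor should justify its choice), and not from the t-test or Wilcoxon p-value.

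In section 3, say which indices objective 1 covers. AUC and trough are the main parameters in section 9.6; Cmax and Tmax can be reported descriptively.

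The change is one of wording, but it has a price. With 8–10 patients and true equality, the 0.80 rule succeeds in 99–100% of trials at CV 10%, but in only 65–75% at CV 20% and 50–59% at CV 25%. Reaching 80% would then take 12 or 17 patients. The sponsor should state a CV and check the cohort size against it. If the power is judged too low, the AUC comparison should be reported as an estimate with its CI, and the non-inferiority wording removed from the objective.

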4. STUDY DESIGN

4.1. Endpoints

Safety and tolerability endpoints

- Frequency of adverse events
- Incidence of adverse reactions to IMP
- Frequency of serious adverse reactions
- Emergence of treatment-emergent adverse events
- The frequency of treatment-emergent adverse events related to infusion rate
- The incidence of administration site reactions
- The frequency of clinically significant deviations in vital signs (blood pressure, body temperature, pulse rate and respiratory rate)
- The frequency of clinically significant deviations in laboratory findings (complete blood count, biochemical findings, markers of intravascular haemolysis, and coagulation parameters)

Safety data are also assessed separately in children and adolescents (after an interim assessment in adults) and compared with the adult data.

Primary pharmacokinetic endpoint:

Mean threshold (trough) plasma concentration of total IgG prior to the next administration of the product, when reaching steady state (after 4 months of treatment), assessed over 6 months.

Primary pharmacokinetic variable:

The monthly trough IgG levels, measured after 4 months of treatment with the IMP, prior to the next infusion, once every 4 weeks, over 6 months, did not fall below the trough levels of the previous therapy with SCIG or IVIG (BIOVEN).

Secondary pharmacokinetic endpoints

These endpoints are tested in the subgroup of subjects aged over 18 years who received treatment with BIOVEN prior to their enrolment in the study and, respectively, throughout the screening period:

- To confirm or calculate the IMP dose adjustment factor when converting from previous IVIG therapy with BIOVEN;

Tested in a subgroup of at least 20 adult patients with PID after approximately 4 months of treatment with the IMP BP-SCIG 20%:

- Area under the concentration-time curve (AUC)
- Maximum concentration (Cmax)
- Time to reach maximum concentration (Tmax)
- The threshold levels of total IgG during the dose titration phase (the dose-effect dependence)
- the *in vivo* elimination half-life
- the elimination constant
- serum clearance
- volume of distribution
- incremental recovery

Secondary endpoints are transformed into corresponding variables.

Primary efficacy endpoint:

Primary efficacy endpoint: The number of serious bacterial infections per subject per year (in order to achieve less than 1.0 infections/subject/year)

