For the variables measured according to the schedule of patient assessments more often than twice, evaluate the changes in quantitative variables over time using a one-way analysis of variance (ANOVA) or rank analysis depending on the normality of the distribution, checked using the Shapiro–Wilk test. In this setting, the dependent variable is the parameter being analysed, and the “visit” factor is the fixed parameter. Evaluate the value and significance for the reliability of the difference between the visits using post hoc analysis with Tukey's test (for ANOVA) or the Wilcoxon signed rank test with Holm's adjustment (for the rank test). To verify the preconditions for the use of analysis of variance, the normal distribution of residuals will be tested using the Shapiro–Wilk test. If the residuals are not distributed normally, a corresponding rank analysis will be performed. Assessment of pharmacokinetic parameters will be informed by fundamental principles of descriptive statistics for the main pharmacokinetic parameters, preliminary assessment of statistical homogeneity of study patient population, as well as by the obtained values for the parameters and the homogeneity of their distribution.

For each patient, individual pharmacokinetic parameters will be calculated:

Cmax, the maximum serum concentration of the analyte;

AUC0-t, the area under the concentration-time PK curve (from zero to last blood sampling, where the concentration of the analyte is higher than or equal to the lower limit of quantification [LLOQ]);

AUC0-∞, the area under the concentration-time PK curve (from zero to infinity).

Tmax, the time to maximum concentration of the analyte;

t1/2, the elimination half-life of the analyte;

Kel, the elimination rate constant of the analyte;

IR, the incremental recovery of class G immunoglobulin;

Vd, volume of distribution;

Cl, serum clearance;

$((AUC_{0-\infty} - AUC_{0-t})/AUC_{0-\infty})$, the residual (extrapolated) area (AUCextrapol).

The values of Cmax and Tmax were calculated using a model-independent method, as the largest of the measured concentrations in each patient and as a corresponding time of observed maximum, respectively.

AUC0-t was calculated using trapezoidal method.

All other parameters were calculated using a model-independent method.

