9.8 Levels of significance

The significance level for the Shapiro–Wilk test and for the primary efficacy variable shall be set at 0.01; for other statistical tests, it shall be set at 0.05.

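### Section 9.6 analyses the monthly IgG troughs visit by visit and leaves the multiplicity correction open between Holm and Benjamini-Hochberg, although Section 4.1 defines the primary PK endpoint as a single six-month mean

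*Protocol*

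**What the plan says.** Section 4.1 gives the primary pharmacokinetic endpoint as one quantity: the mean trough concentration of total IgG at steady state, assessed over six months. The primary pharmacokinetic variable just below it is worded by month: the monthly levels "did not fall below the trough levels of the previous therapy with SCIG or IVIG (BIOVEN").

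Section 9.6 follows the monthly wording. The troughs taken "prior to the next infusion, once every 4 weeks, over 6 months, shall be compared with the trough levels for at least two prior infusions", meaning infusions given with the earlier product. For two visits it names a paired t-test or Wilcoxon signed rank test. For more than two visits it names one-way ANOVA followed by Tukey, with a rank analysis as fallback for which it names no adjustment. It then states: "For the Shapiro-Wilk test, the significance level will be set at 0.01, and for other tests it will be set at 0.05". The multiplicity sentence follows: "If a multiple comparisons effect occurs", then "significance level adjustments will be applied using the Holm method or Benjamini-Hochberg method". It gives no rule for choosing between the two methods, defines no family of tests and does not explain the trigger.

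Section 9.7, on the group of 20 adults with full profiles, names only the "Wilcoxon signed rank test with Holm's adjustment (for the rank test"). Sections 9.4 and 9.5 do the same for efficacy and laboratory variables. Section 9.8 repeats the level: "for other statistical tests, it shall be set at 0.05".

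Section 3 lists, among the additional PK objectives, a between-cohort comparison that begins "To compare the results of pharmacokinetic parameter study" and names ten parameters.

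**The concern.** Holm controls the probability of any false rejection in a family. Benjamini-Hochberg controls the expected share of false rejections among those made. They are not interchangeable, and Section 9.6 offers both without saying when either applies. The trigger does not help, because multiplicity follows from how many tests are planned; it is not something observed in the data.

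The section covers the comparison behind the primary PK variable. Success there means that troughs did not fall, so a stricter correction makes the favourable statement easier to reach. For a claim that parameters differ, the looser correction helps. Two readers applying Section 9.6 correctly could report different numbers of months with lower troughs from the same data.

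The more basic issue is that most of this multiplicity need not exist. The endpoint in Section 4.1 is one mean per patient, and Section 9.6 provides no test of that mean.

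**Working it through.** The protocol gives no power or error-rate figure for this step, so there is nothing of its own to reproduce.

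**Inputs.** Level 0.05 (Sections 9.6 and 9.8). The side of the test is not stated; two-sided is assumed. Number of monthly comparisons m = 6, from one every four weeks over six months (7 if both ends of the window count). At least 40 patients with troughs (Section 4.2). Effect sizes and correlations between months are assumptions, because the protocol gives none.

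**Thresholds at m = 6, smallest p-value first.**

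| Rank i | Holm, 0.05/(7 − i) | Benjamini-Hochberg, 0.05·i/6 |
|---|---|---|
| 1 | 0.0083 | 0.0083 |
| 2 | 0.0100 | 0.0167 |
| 3 | 0.0125 | 0.0250 |
| 4 | 0.0167 | 0.0333 |
| 5 | 0.0250 | 0.0417 |
| 6 | 0.0500 | 0.0500 |

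Holm steps down from the smallest p-value and stops at the first failure. Benjamini-Hochberg rejects everything up to the largest rank that meets its threshold. So if all six p-values lie above 0.0083 and at or below 0.05, Holm rejects none and Benjamini-Hochberg rejects six. An example is 0.012, 0.018, 0.024, 0.030, 0.036, 0.045. This shows that the extreme is possible, not that it is likely.

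**How often the methods disagree.** Six equally correlated normal statistics with a true common fall, expected z 2.0 to 2.5 per month, correlation 0.5 to 0.7:

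- different number of months declared lower: about 22 to 28% of trials;
- Benjamini-Hochberg finds at least one month, Holm none: 2.5 to 3.9%;
- six months against none: 0.07 to 0.3%.

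A separate simulation with paired t-tests in 40 patients, falls of 0.2 to 0.5 SD and correlation 0.5 or 0.8 gave about 11 to 31%, 1.5 to 5% and 0.05 to 0.8%.

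**Family-wise error when half the tests are truly different.** With the real effects at z = 5, Benjamini-Hochberg gives about 0.09 to 0.10 for six tests and 0.115 to 0.14 for ten; Holm stays between 0.04 and 0.05. That effect size is close to the worst case. At z = 2.0 to 2.5, Benjamini-Hochberg gives only about 0.05 to 0.09 across both family sizes.

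**The single contrast.** A patient's six-month mean trough minus the mean previous-product trough is the average of the six month-minus-prior differences. If each month has expected z and the months correlate at ρ, the contrast has expected z/√((1 + 5ρ)/6), and its power at two-sided 0.05 is Φ(that value − 1.96).

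- ρ = 0.5: √(3.5/6) = 0.764. z = 2.0 gives 2.0/0.764 = 2.62, power 0.74. z = 2.5 gives 3.27, power 0.91.
- ρ = 0.7: √(4.5/6) = 0.866. z = 2.0 gives 2.31, power 0.64. z = 2.5 gives 2.89, power 0.82.

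Over the same four scenarios, the chance that Holm declares any month lower is about 52 to 82%. The single contrast is therefore more likely to reveal a real common fall, and it needs no correction.

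**The case against.** The strongest reply is that Section 9.6 has already chosen for the main case. Monthly troughs plus at least two prior values are more than two visits, so the named route is ANOVA with Tukey, which handles its own pairwise comparisons. This stands. It confines the open choice to the rank fallback, to paired month-versus-prior tests if those are run, and to families of several PK parameters.

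Three stronger readings are tempting, and the protocol does not support them.

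- A reader might infer that the same troughs will plausibly show six falls or none. The arithmetic allows it, but it happened in under 1% of simulated trials.
- A reader might infer that the sponsor can pick the method after seeing results. The protocol fixes no choice, but a statistical analysis plan not shown here may do so, and Section 9.1 gives the analysis to a contracted third-party biostatistician.
- A reader might infer that Benjamini-Hochberg breaches the 0.05 of Section 9.8. That section gives a level for each test and does not call it family-wise. False discovery control is defensible for secondary PK parameters.

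It can also be said that naming Holm alone is detail an analysis plan would settle, and that Holm makes a statement of no fall easier. Both are fair, and they are why the remedy rests on the single contrast. The primary efficacy test, at 0.01, is not affected.

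**Conclusion.** The point holds at minor severity. Section 9.6 treats two non-equivalent corrections as alternatives behind an undefined trigger, does not match Sections 9.4, 9.5 and 9.7, and analyses by visit an endpoint that Section 4.1 defines as one mean. Where Tukey does not apply, the choice changes the number of months declared lower in roughly a quarter of trials, but changes some against none in only about 2.5 to 4%. These rates rest on assumed effects and correlations, equal correlation between months and two-sided tests at 0.05. That Section 4.1 already supplies a single quantity to test rests on the text alone.

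**What to change.** In Section 9.6, make the primary trough analysis one paired contrast for previously treated patients: each patient's six-month mean trough against the mean of that patient's previous-product troughs, with a confidence interval and no multiplicity correction. Report individual months descriptively. Treatment-naïve patients keep the descriptive literature comparison already planned. Reword the primary PK variable in Section 4.1 so that it refers to the six-month mean, in line with the endpoint above it.

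For any PK family still tested, delete the conditional trigger and the Benjamini-Hochberg alternative, and name Holm, as in Sections 9.4, 9.5 and 9.7. Label the between-cohort comparison of ten parameters exploratory.

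The cost is small wording changes in Sections 4.1 and 9.6 and slightly less power in the exploratory PK family. No visit, sample or patient procedure changes. The interval shows how large a fall the data exclude, which a non-significant test of change does not.
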